10. PHARMACOKINETIC / PHARMACODYNAMIC ANALYSES

Any exploratory pharmacokinetic/pharmacodynamic analyses only consider exploratory endpoints and will be analyzed and reported separately.

11. ADDITIONAL ANALYSES DUE TO THE COVID-19 PANDEMIC

11.1. Study Population

11.1.1. Subject Disposition

The ‘Summary of Subject Status and Subject Disposition for the Study Conclusion Record’ and the ‘Summary of Treatment Status and Reasons for Discontinuation of Study Treatment’ will be repeated, with the reason for withdrawal/discontinuation categorized as due to the COVID-19 pandemic, or non-due to the COVID-19 pandemic based on information collected on the COVID-19 Pandemic Study Impact form. The summaries will be based on GSK Core Data Standards, and details are provided in [Appendix 10](#).

11.1.2. Protocol Deviations

In addition to the overall summary of important protocol deviations, separate summaries will be produced of important protocol deviations related to COVID-19, and important protocol deviations not related to COVID-19. A listing of non-important protocol deviations related to COVID-19 will also be produced.

Visits and assessments missed due to the COVID-19 pandemic, together with visits conducted remotely, will be listed by subject. The summaries will be based on GSK Core Data Standards, and details are provided in [Appendix 10](#)

11.1.3. Additional Displays for Participants with a COVID-19 Infection

A participant is defined as having a suspected, probable or confirmed COVID-19 infection during the study if the answer is “Confirmed”, “Probable” or “Suspected” to the case diagnosis question from the COVID-19 coronavirus infection assessment eCRF.

A listing of the participants with a suspected, probable or confirmed COVID-19 infection, and of COVID-19 test results will be based on GSK Core Data Standards. The details of the planned displays are provided in [Appendix 10](#)

11.2. Safety

11.2.1. Assessment of COVID-19 AEs

A Standardised MedDRA Query (SMQ) will be used to identify all COVID-19 AEs.

The incidence of AEs and SAEs (Fatal and Non-Fatal) of COVID-19, COVID-19 AEs leading to study drug discontinuation, and COVID-19 AEs leading to study withdrawal, and COVID-19 AEs by severity, will be obtained from standard AE and SAE summaries.

11.2.2. Impact of COVID-19 Pandemic on Safety Results

Since this single-site, United States-based, study began enrolment after the COVID-19 pandemic began, the beginning of pandemic measures in the United States had no effect on the safety results. Therefore, separate AE summaries and listings before and after the pandemic start are not produced.

13. APPENDICES

13.1. Appendix 1: Exclusions from Analysis Populations

Any analysis population exclusions, due to protocol deviations, will be discussed by the study team and documented.

13.2. Appendix 2: Schedule of Activities

13.2.1. Protocol Defined Schedule of Events

Please refer to Protocol Section 1.2.

13.3. Appendix 3: Assessment Windows**13.3.1. Definitions of Assessment Windows for Analyses**

All acceptable assessment windows are defined in Section 4.1 (dosing), Section 8.1.4 (ECG), of the protocol and the study reference manual. No assessment windows are redefined in the RAP.

13.4. Appendix 4: Study Phases and Treatment Emergent Adverse Events

13.4.1. Study Phases

Assessments and events will be classified according to the time of occurrence relative to treatment administration(s).

Study Phase	Definition
Pre-Treatment	Date < Study Treatment Start Date
On-Treatment	Study Treatment Start Date ≤ Date ≤ Study Treatment Stop Date + 22 days
Post-Treatment	Date > Study Treatment Stop Date + 22 days

13.4.1.1. Study Phases for Concomitant Medication

Study Phase	Definition
Prior	If medication end date is not missing and is before 28 days prior to screening visit
Concomitant	Any medication that is not a prior

NOTES:

- Please refer to [Appendix 7: Reporting Standards for Missing Data](#) for handling of missing and partial dates for concomitant medication. Use the rules in this table if concomitant medication date is completely missing.

13.4.2. Treatment Emergent Flag for Adverse Events

Flag	Definition
Treatment Emergent	
 • If AE onset date is on or after treatment start date & on or before treatment stop date. (plus washout or protocol-specified time limit (e.g. half-life of drug, certain number of days, etc.). • Study Treatment Start Date ≤ AE Start Date ≤ Study Treatment Stop Date [+ 22 days]. • For studies with greater than one treatment period (e.g., crossover study) and the dates of changes in grade are collected, if AE onset is during one period and worsens during a later period it would be counted in both periods. For the initial period the logic would be as above. For the later period the logic would use the treatment dates associated with the later period: • Treatment Period Start Date ≤ AE Worsening Date ≤ Study Treatment Stop Date [+ 22 days].

NOTES:

- If the study treatment stop date is missing, then the AE will be considered to be On-Treatment.
- Time of study treatment dosing and start/stop time of AEs should be considered, if collected.

13.5. Appendix 5: Data Display Standards & Handling Conventions

13.5.1. Reporting Process

Software	

 The currently supported versions of SAS software 9.4 or higher will be used. 	
Reporting Area	
HARP Server	:\\us1salx00259.corpnet2.com
HARP Compound	:\\arwork\\gsk3739937\\mid212548\\final_01
Analysis Datasets	

 Analysis datasets will be created according to CDISC standards (SDTM IG Version 3.2 & ADaM IG Version 1.1]. 	
Generation of RTF Files	

 RTF files will be generated for Tables, one RTF file per item. Listings will be generated in L10 format, and Figures will be generated in PDF format. 	
Generation of xlm Files	

 xlm files will not be generated for the current reporting efforts 	
Dictionaries	

 The current dictionary version in effect at the time of reporting will be used Adverse Events MedDRA 24.0 Concomitant Medications GSKDRUG v 1.9 and WHODrug GLOBAL C3 March 1, 2020 	

13.5.2. Reporting Standards

General	

 The current GSK Statistical Display Standards in the GSK Standards Library (IDSL) will be applied for reporting, unless otherwise stated (Library Location: https://spope.gsk.com/sites/IDSLLibrary/SitePages/Home.aspx): Do not include participant level listings in the main body of the GSK Clinical Study Report. All participant level listings should be located in the modular appendices as ICH or non-ICH listings 	
Formats	

 GSK Statistical Display Principles (5.03 & 6.06.3) for decimal places (DP's) will be adopted for reporting of data based on the raw data collected, unless otherwise stated. Numeric data will be reported at the precision collected on the eCRF. The reported precision from non eCRF sources will follow the GSK Standard Statistical Display Principles but may be adjusted to a clinically interpretable number of DP's. 	
Planned and Actual Time	

 Reporting for tables, figures and formal statistical analyses: 
 Planned time relative to dosing will be used in figures, summaries, statistical analyses and calculation of any derived parameters, unless otherwise stated. The impact of any major deviation from the planned assessment times and/or scheduled visit days on the analyses and interpretation of the results will be assessed as appropriate. Reporting for Data Listings: 
 Planned and actual time relative to study drug dosing will be shown in listings (Refer to GSK Standard Statistical Display Principle 5.05.1). 	

 Unscheduled or unplanned readings will be presented within the participant's listings. 	
Unscheduled Visits	

 Unscheduled visits will not be included in summary tables and/or figures. All unscheduled visits will be included in listings. 	
Descriptive Summary Statistics	
Continuous Data	Refer to GSK Standard Statistical Display Principle 6.06.1
Categorical Data	N, n, frequency, %
Graphical Displays	

 Refer to GSK Standard Statistical Display Principles 7.01 to 7.13. 	

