7.1.2. QTc Stopping Criteria

The QTcF *must* be used for *each individual participant* to determine eligibility for and discontinuation from the study. This formula may not be changed or substituted once the participant has been enrolled.

The QTcF stopping criteria is based on averaged QTcF values of triplicate electrocardiograms obtained over a brief (e.g., 5-10 minute) recording period.

A participant that meets either bulleted criterion based on the average of triplicate ECG readings will be withdrawn from study treatment.

- QTcF >500 msec,
- Change from baseline: QTcF >60 msec

See the [SoA](#) for data to be collected at the time of intervention discontinuation and follow-up and for any further evaluations that need to be completed.

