8.1.4. Electrocardiograms

- In Part 1, 12-Lead ECG will be performed on Day-1, Day 1 at pre-dose, and 1, 2, 4, 6, 12 and 16 hours post-dose. At all other timepoints, ECG will be performed at the pre-dose timepoint.
- In Part 2, 12-Lead ECG will be performed at the pre-dose timepoint at all timepoints indicated in SoA.
- In Part 3, 12-Lead ECG should be performed on Day 1 in Periods 1-3 at pre-dose, 2 h, and h post dose. Pre-dose ECGs in Periods 1-3 will be taken in triplicate.
- Triplicate 12-lead ECG recordings will be obtained after the participant has been in a semi-supine position for at least 5 minutes using an ECG machine that automatically calculates the heart rate and measures PR, QRS, QT, and QTc intervals. Participant eligibility will be based upon triplicate ECG recordings. Single recordings will be made at all other timepoints.
- At each time point at which triplicate ECG are required, 3 individual ECG tracings will be obtained as closely as possible in succession, but no more than 2 minutes apart. The full set of triplicates should be completed in less than 4 minutes.
- If any abnormalities in ECG interval are noted (including prolongation of the QT interval), ECGs will be repeated in triplicate with recordings over a 5 minute time period. Refer to Section [7.1.2](#) for QTc Stopping Criteria and additional QTc readings that may be necessary.
- At least one of these ECGs will be available and reviewed by the PI on site to evaluate for QT prolongation to ensure subject safety. Additional safety ECGs beyond those described in the [SoA](#) may be printed at the discretion of the PI if prolongation in QT interval is suspected.
- Safety ECGs may be printed from the Global Instrumentation Holter device (see below). ECG parameters from safety ECGs will not be collected unless as part

of an observed adverse events. Refer to Section 7.1.2 for QTc Stopping Criteria and additional QTc readings that may be necessary.

- At timepoints for ECG extraction from Holter recordings, participants will be semi-supinely resting for at least 10 minutes.
- Once human data (eg Cmax) is known, the number of ECG time points may be reduced in subsequent dosing groups.
- Additional detail can be found in the SRM.

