5.2. Baseline Definitions

For all endpoints (except as noted in baseline definitions) the baseline value will be the latest pre-dose assessment with a non-missing value, including those from unscheduled visits. If time is not collected, Day 1 assessments are assumed to be taken prior to first dose and used as baseline.

Part 1 (SAD Cohorts 1 and 2)

Parameter	Study Assessments Considered as Baseline			Baseline Used in Data Display
	Screening	Day -1	Day 1 (Pre-Dose)	
Lab	X	X		Day -1
ECG	X	X	X	Day 1 (Pre-Dose)
Vital Signs	X	X	X	Day 1 (Pre-Dose)

Part 2 (MAD Cohorts 3, 4, 5, and 6)

Parameter	Study Assessments Considered as Baseline			Baseline Used in Data Display
	Screening	Day -1	Day 1 (Pre-Dose)	
Lab	X	X	X	Day 1 (Pre-Dose)
ECG	X	X	X	Day 1(Pre-Dose)
Vital Signs	X	X	X	Day 1 (Pre-Dose)

Part 3 (RBA/FE)

Parameter	Study Assessments Considered as Baseline			Baseline Used in Data Display
	Screening	Day -1	Day 1 (Pre-Dose)	
Lab	X	X		Day -1
ECG	X	X	X	Day 1 (Pre-Dose)
Vital Signs	X	X	X	Day 1 (Pre-Dose)

On Day 1 triplicate pre-dose ECGs will be performed. The baseline for every ECG parameter will be calculated as the average of that parameter's values from the Day 1 pre-dose triplicate ECG reading

On Day 1 three readings of blood pressure and pulse will be taken. The first reading will be rejected. The average of the second and third readings (as recorded in the CRF) will serve as baseline.

Unless otherwise stated, if baseline data is missing no derivation will be performed and baseline will be set to missing.

For Part 3, baseline will be rederived for each period.

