13.7. Appendix 7: Reporting Standards for Missing Data

13.7.1. Premature Withdrawals

Element	Reporting Detail
General	
 Participant study completion was defined as complete if he/she has completed all phases of the study including the last visit and the last scheduled procedure shown in the schedule of activities Withdrawn participants may be replaced in the study depending on study part and whether adequate sample size for a cohort as already been reached. All available data from participants who were withdrawn from the study will be listed and all available planned data will be included in summary tables and figures, unless otherwise specified.

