3.14.	Safety	AE5B	Summary of Adverse Events of Special Interest by Maximum Grade by System Organ Class and Preferred Term – Part 2	Use GSK3640254 SRT spreadsheet at time of reporting to identify AESI	SAC [1]
3.15.	Safety	AE5B	Summary of Adverse Events of Special Interest by Maximum Grade by System Organ Class and Preferred Term – Part 3	Use GSK3640254 SRT spreadsheet at time of reporting to identify AESI	SAC [1]
Serious and Other Significant Adverse Events					
3.16.	Safety	AE16	Summary of Serious Adverse Events by System Organ Class and Preferred Term (Number of Subjects and Occurrences) – Part 1	FDAAA, EudraCT	SAC [1], HL
3.17.	Safety	AE16	Summary of Serious Adverse Events by System Organ Class and Preferred Term (Number of Subjects and Occurrences) – Part 2	FDAAA, EudraCT	SAC [1], HL
3.18.	Safety	AE16	Summary of Serious Adverse Events by System Organ Class and Preferred Term (Number of Subjects and Occurrences) – Part 3	FDAAA, EudraCT	SAC [1], HL

Safety: Tables					
No.	Population	GSK Standard/ Example Shell	Title	Programming Notes	Deliverable [Priority]
3.19.	Safety	AE1	Summary of Adverse Events Leading to Permanent Discontinuation of Study Treatment or Withdrawal from Study by System Organ Class and Preferred Term – Part 1	GSK Statistical Display Standard	SAC [1], HL
3.20.	Safety	AE1	Summary of Adverse Events Leading to Permanent Discontinuation of Study Treatment or Withdrawal from Study by System Organ Class and Preferred Term – Part 2	GSK Statistical Display Standard	SAC [1], HL
3.21.	Safety	AE1	Summary of Adverse Events Leading to Permanent Discontinuation of Study Treatment or Withdrawal from Study by System Organ Class and Preferred Term – Part 3	GSK Statistical Display Standard	SAC [1], HL
Laboratory: Chemistry					
3.22.	Safety	LB1	Summary of Chemistry Changes from Baseline	ICH E3, Page by Part	SAC [1], HL
3.23.	Safety	LB15A	Summary of Worst Case Chemistry Results Relative to Normal Range Post-Baseline Relative to Baseline	ICH E3	SAC [1]
Laboratory: Hematology					
3.24.	Safety	LB1	Summary of Haematology Changes from Baseline	ICH E3, Page by Part	SAC [1], HL
3.25.	Safety	LB15A	Summary of Worst Case Haematology Results Relative to Normal Range Post-Baseline Relative to Baseline	ICH E3, Page by Part	SAC [1]
Laboratory: Urinalysis					
3.26.	Safety	UR1	Summary of Worst Case Urinalysis Results Post-Baseline Relative to Baseline – Part 1	ICH E3, For discrete or character values only	SAC [1], HL

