3.27.	Safety	UR1	Summary of Worst Case Urinalysis Results Post-Baseline Relative to Baseline – Part 2	ICH E3, For discrete or character values only	SAC [1], HL

Safety: Tables					
No.	Population	GSK Standard/ Example Shell	Title	Programming Notes	Deliverable [Priority]
3.28.	Safety	UR1	Summary of Worst Case Urinalysis Results Post-Baseline Relative to Baseline – Part 3	ICH E3, For discrete or character values only	SAC [1], HL
ECG					
3.29.	Safety	EG1	Summary of ECG Findings - Part 1	GSK Statistical Display Standard	SAC [1]
3.30.	Safety	EG1	Summary of ECG Findings – Part 2	GSK Statistical Display Standard	SAC [1]
3.31.	Safety	EG1	Summary of ECG Findings – Part 3	GSK Statistical Display Standard	SAC [1]
3.32.	Safety	EG10A	Summary of Maximum QTc Values Post-Baseline Relative to Baseline by Category	GSK Statistical Display Standard, ICH E14, page by part	SAC [1], HL
3.33.	Safety	EG2	Summary of Change from Baseline in ECG Values by Visit	GSK Statistical Display Standard, page by part	SAC [1]
3.34.	Safety	EG11A	Summary of Maximum Increase in QTc Values Post-Baseline Relative to Baseline by Category	GSK Statistical Display Standard, page by part	SAC [1], HL
Vital Signs					
3.35.	Safety	VS3A	Summary of Vital Sign Shifts from Baseline Relative to Potential Clinical Importance (PCI) Criteria	GSK Statistical Display Standard, page by part	SAC [1], HL

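### SAP 13.5.2 keeps unscheduled visits out of every summary table, so the maximum-QTc, worst-case and PCI-shift tables can miss an extreme, or a first abnormality, seen only off schedule

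*SAP*

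**What the plan says.** SAP 13.5.2 gives two rules for unscheduled visits. For summaries: "Unscheduled visits will not be included in summary tables and/or figures". For listings: "All unscheduled visits will be included in listings". SAP 13.7.1 takes a similar line for withdrawn participants: "all available planned data will be included in summary tables and figures, unless otherwise specified".

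Baseline is treated differently. Under SAP 5.2, "the baseline value will be the latest pre-dose assessment with a non-missing value, including those from unscheduled visits".

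SAP 13.10.5 plans several displays of extremes, among them Table 3.32, "Summary of Maximum QTc Values Post-Baseline Relative to Baseline by Category", and Table 3.23, "Summary of Worst Case Chemistry Results Relative to Normal Range Post-Baseline Relative to Baseline". Tables 3.25 (haematology), 3.26-3.28 (urinalysis), 3.34 (largest QTc increase) and 3.35 (vital-sign shifts against PCI limits) are of the same kind.

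The protocol plans repeat tests after an abnormal finding. In Protocol 8.1.4, an abnormal ECG interval means that "ECGs will be repeated in triplicate with recordings over a 5 minute time period", while routine ECGs outside the named triplicate time points are single recordings. Protocol 7.1.2 adds: "The QTcF stopping criteria is based on averaged QTcF values of triplicate electrocardiograms". Protocol 8.1.5 has clinically significant laboratory abnormalities repeated until they settle. Appendix 5 requires repeat liver chemistry within 24 or 24-72 hours, then twice weekly or weekly. Protocol 1.2 foresees unscheduled safety samples.

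**The concern.** A table of maxima is useful only if it draws on all post-baseline values. Here the rule removes the class of assessment most likely to follow a worrying result. Safety is a primary endpoint in all three parts, and QT prolongation is both a named risk in Protocol 2.3 and an event of special interest in SAP 7.1. The post-dose QTcF that decides a stop will normally come from an added triplicate, because the scheduled post-dose recording is single.

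If that triplicate counts as unscheduled, a participant could be withdrawn on a value that the maximum-QTc table does not contain. Tables 3.26-3.28, 3.32, 3.34 and 3.35 are also marked for headline data delivery, so they are among the first results read.

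**Working it through.** The plan gives no figure to reproduce. The check is of the text, with a small illustration of size.

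1. **Is there an exception?** SAP 5.2, 7.2, 7.3, 13.5.2, 13.6.1, 13.7.1 and 13.8 and the programming notes to Tables 3.22-3.35 were searched. Only the baseline definition admits unscheduled values. SAP 13.6.1 mentions a row for any post-baseline visit but does not say that it includes unscheduled ones, so it does not override 13.5.2.

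2. **Direction.** For a fixed baseline, the maximum over scheduled values is at most the maximum over all values, and the minimum is at least the overall minimum. Dropping values can leave the category unchanged or move it towards normal, never the other way.

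3. **What each table can lose.**
   - Tables 3.32 and 3.34: a higher QTc category reached only on repeat testing. The category cut-points are in sponsor display standards outside the documents.
   - Tables 3.26-3.28: a worse urinalysis result seen only off schedule.
   - Table 3.35: a first crossing of a PCI limit seen only off schedule.
   - Tables 3.23 and 3.25: only an abnormality, or a change of direction, first seen off schedule. SAP 13.6.1 counts participants as High, Low or both. If a scheduled value was already above range, a still higher repeat changes nothing.

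4. **Weight of one participant.** Active numbers are 6 per SAD period and 7 per MAD cohort (Protocol 4.1), and 12 evaluable to 18 treated in Part 3.
   - 1/6 = 16.7%; 1/7 = 14.3%
   - 1/12 = 8.3%; 1/18 = 5.6%

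   A missed participant turns that percentage into 0%. These are weights, not probabilities.

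5. **Same-time-point repeats.** Take hypothetical values: a scheduled single QTcF of 485 ms, then a repeat triplicate averaging 505 ms, above the >500 ms limit in Protocol 7.1.2.
   - Repeat treated as an unscheduled visit (13.5.2): the table uses 485 ms.
   - Repeat treated as a multiple measurement at one time point (13.6.1), pooling all four readings: (485 + 3 × 505)/4 = 2000/4 = 500.0 ms, which is not above 500.
   - Triplicate averaged within itself and included: 505 ms.

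   The SAP does not say which of the first two applies. In this example both lose the stop-level value.

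**The case against.** The strongest reply is that nothing would be hidden. Clinically significant ECG and laboratory abnormalities are adverse events under Appendix 3. They would appear in the tables of all events (3.1-3.3), events of special interest (3.13-3.15) and events leading to discontinuation (3.19-3.21). Listing 25 gives all ECG values for anyone with a PCI value, and Listings 15 and 31-33 cover laboratory toxicity and liver events. With 6 or 7 active participants per dose, reviewers rely heavily on listings. All of this stands, and it limits the consequence. It does not correct a table labelled as a maximum, and SAP 13.5.2 keeps participant listings out of the main body of the report.

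Three stronger readings are tempting but not supported:

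- **That laboratory tables would drop participants whose abnormal result prompted a repeat.** A scheduled trigger is still counted in Tables 3.23 and 3.25. The liver follow-up schedule adds nobody to Table 3.23 in that case.
- **That a confirmatory triplicate is certainly excluded.** The rule names visits. A repeat minutes later at a scheduled time point may fall under 13.6.1 instead.
- **That all the data are already in hand.** This is reasonable for laboratory values. Protocol 8.1.4, however, limits collection of safety-ECG parameters to those forming part of an adverse event. The documents also do not clearly say whether safety ECGs or Holter extractions feed Tables 3.32 and 3.34.

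The sponsor's display standards might include unscheduled values, but 13.5.2 applies them only where nothing else is stated, and here something is. The contrast with baseline also matters less for ECGs, whose baseline is the Day 1 pre-dose triplicate mean.

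**Conclusion.** The point holds as a reporting flaw. As written, the SAP allows tables of maxima, worst cases and PCI shifts to omit the true extreme, and the error can only flatter the safety profile. The effect is potentially widest for QTc and narrowest for Tables 3.23 and 3.25. One affected participant changes a Part 1 or Part 2 active-group cell by 14.3 to 16.7 percentage points.

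This rests on reading 13.5.2 literally and on repeat assessments being recorded as unscheduled. The expected number of affected participants cannot be derived, and the 485/505 ms case is only an illustration. A reader might infer that dose escalation or individual stopping is compromised. It is not: those decisions are made during the study under Protocol sections 4.3.6 and 7.1 and do not depend on these tables.

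**What to change.** - Amend SAP 13.5.2 so that unscheduled post-baseline values are excluded from by-visit summaries only and are included in Tables 3.23, 3.25-3.28, 3.32, 3.34 and 3.35. Align SAP 13.7.1.
- State in SAP 13.6.1 that a repeat triplicate is averaged within itself and not pooled with the single reading that triggered it.
- Confirm that repeat safety-ECG values are captured in the database, given the limit in Protocol 8.1.4, and state which ECG source feeds Tables 3.32 and 3.34.

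By-visit summaries keep the exclusion. The cost is a few SAP sentences and a programming flag. Laboratory values should need no new data, since unscheduled visits are already to be listed. For ECGs the cost depends on the capture check.
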